10.1 Primary Endpoint Definition

The primary objective of this study is to describe the expected real-world usage duration of Levosert for its different indications.

Duration of Levosert usage is defined as the difference in time between removal (with or without replacement) and insertion of the device. In the absence of detailed patient-level data and in the context of this survey, expected duration of Levosert usage for each indication will be calculated as follows:

Expected usage duration of Levosert (years)

$$= \sum_{i=1}^{6} (i \ x \ likelihood \ of \ Levosert \ removal \ in \ Year \ i)$$

+ (likelihood of Levosert removal beyond Year 6 x total expected usage duration in those patients)

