10.2 Determination of Sample Size

A convenience sampling approach was chosen aiming to reach a sufficiently large group of eligible HCPs who have collectively treated a substantial number of patients with Levosert for the HMB indication.

Based on the size and composition of the physician panel in the four study countries, it is estimated that a sample of approximately 380 HCPs would qualify to complete the questionnaire. Assuming an estimated 27,500 Levosert removals (from product launch until 2020) by approximately 11,200 OB-GYNs across the study countries (average 2.46 Levosert removals per OB-GYN), a sample of approximately 380 HCPs would achieve collective experience with the removal of approximately 820 Levosert IUS. Assuming an approximately balanced distribution by both indications – i.e., contraception only vs. HMB with and without intended contraception: 45% and 55%, respectively (Römer et al., 2009) –, this sample would cover approximately 450 Levosert removals in patients with HMB. Coverage of such a level of collective experience is deemed sufficient to generate a robust estimate on the expected duration of Levosert usage.

See Appendix 1 for detailed data supporting this convenience sampling approach.

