10.3 Data Analysis

All analyses will be descriptive in nature. Categorical variables will be summarized using counts and percentages. Continuous variables will be summarized using the number of observations (n), mean, standard deviation (SD), median, minimum, and maximum, interquartile ranges (IQR), and 95% confidence intervals (CI), as appropriate. In addition, utilization patterns of Levosert will be visualized using plots or similar techniques.

1. Geographical distribution of Prescribers (by country)

- 2. Count and percentage of Prescribers by ranges of their professional time spent on direct patient care
- 3. Count and percentage of Prescribers by duration of their medical practice
- 4. Count and percentage of Prescribers by practice setting
- 5. Count and percentage of Prescribers having prescribed each brand of levonorgestrel IUS
- 6. Count and percentage of Prescribers having experience removing each brand of levonorgestrel (with or without replacement)
- 7. Descriptive statistics on Prescribers' count of IUS prescriptions in the past 10 years
- 8. Descriptive statistics on Prescribers' count of Levosert prescriptions and removals (with or without replacement), by indication
- 9. Descriptive statistics on Prescribers' count of patients they personally manage in a typical month without COVID-19 restrictions
- 10. Descriptive statistics on percentage of Prescribers' patients by type of contraception, by indication
- 11. Descriptive statistics on percentage of Prescribers' patients using IUSs who are receiving Levosert, by indication
- 12. Distribution of Prescriber's patients at the time of Levosert prescription among age categories, by indication
- 13. Count and percentage of Prescribers among categories of duration-of-effectiveness of Levosert for heavy menstrual bleeding
- 14. Percentage of Prescribers' patients getting Levosert removed by the end of each year, by indication
- 15. Descriptive statistics on the total duration of use of Levosert in patients who use Levosert for more than six years, by indication
- 16. Percentage of Prescribers' patients who use Levosert for heavy menstrual bleeding indication who would continue to show treatment effectiveness by the end of each year
- 17. Distribution of Prescribers' patients among reason-for-removal categories, by indication
- 18. Count and percentage of Prescribers by overall level of satisfaction with Levosert in patients who use it for three or more years, by indication

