Appendix 1: Supporting Data for HCP Sample Size Determination

A feasibility assessment was conducted to understand the estimated number of Levosert removals since product launch in each country, the total number of practicing OB-GYNs, and the expected number of OB-GYNs that could be recruited from a large physician panel across the study countries (i.e., OB-GYNs who would be eligible and willing to participate).

The number of Levosert removals in the countries of interest has been estimated from:

- 1. The number of pharmacy-level Levosert sales per country and per year from product launch in 2014 until the last full year of product sales which is 2020 (IMS pharmacy sales database, 2021).
- 2. LNG-IUS user retention after 1 to 5 years of usage as reported by a post-marketing study: 0.94, 0.87, 0.82, 0.76, 0.65, respectively (Backman et al., 2001). For years outside the reported years, 0% retention is assumed resulting in a conservative estimate.

Table 2. Levosert Removals Sin	ce Proc	luct Lau	nch, Es	stimatio	n
Country	2020	2019	2018	2017	- 2

	Country	2020	2019	2018	2017	2016	2015	2014	Total
Czech	Sold	5,803	5,320	5,206	4,233	4,326	2,768	99	27,755
Republic	Removed since (estimated)	348	692	937	1,016	1,514	2,768	99	7,374
	Sold	8,736	11,765	8,971	9,282	8,619	7,931	40	55,344
Poland	Removed since (estimated)	524	1,529	1,615	2,228	3,017	7,931	40	16,884
	Sold	690	907	805	794	907	323	0	4,426
Serbia	Removed since (estimated)	41	118	145	191	317	323	0	1,135
	Sold	1,771	1,824	1,733	1,469	1,485	549	3	8,834
Slovakia	Removed since (estimated)	106	237	312	353	520	549	3	2,080
τ	Jser retention (estimated)	94%1	87%²	82%2	76%²	65%²	0%	0%	

The number of practicing OB-GYNs per country has been estimated based on data from multiple sources (WHO 2021, LKCR 2022, NIL 2021)

Distribution by indications has been estimated based on a multinational LNG-IUS patient survey, which showed that 55% of removals were in patients where IUS was prescribed for heavy menstrual bleeding and the remaining 45% for contraception (Römer et al., 2009).

A summary of Levosert sales and removals from product launch until 2020 in the four study countries, the geographical distribution of OB-GYNs, the expected achievable sample of OB-

-

¹ Based on epidemiological survey of 23,885 LNG-IUS users (Backman et al., 2001).

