Appendix 2: Screener

S1. In which country is your primary practice located?

1	Poland	POLAND QUOTA=150
2	Czech Republic	CZECH REPUBLIC QUOTA=80
3	Serbia	SERBIA QUOTA=100
4	Slovakia	SLOVAKIA QUOTA=50
98	Other (specify)	TERMINATE

S2. What is your role within your practice?

1	Physician	CONTINUE
2	Nurse	TERMINATE
98	Other (specify)	TERMINATE

S3. What is your primary state-certified medical specialty?

1	General Practice/Internal Medicine	TERMINATE
2	Dermatology	TERMINATE
3	Endocrinology	TERMINATE
4	Gynecology and Obstetrics	CONTINUE
98	Other (specify)	TERMINATE

S4. Approximately what percent of your professional time is spent on direct patient care, as opposed to teaching, research, or administrative roles?

1	Less than 25% of the time	TERMINATE
2	25-50% of the time	CONTINUE
3	51-75% of the time	CONTINUE
4	More than 75% of the time	CONTINUE

S5. How many years have you been practicing Gynecology and Obstetrics since gaining this specialization?

1	0 - 3 years	TERMINATE
2	4 - 10 years	CONTINUE
3	11 - 20 years	CONTINUE
4	More than 20 years	CONTINUE
97	I am not a certified specialist yet	TERMINATE

S6. Which of the following intrauterine systems (IUSs) have you prescribed to your patients? *Please select all that apply.*

1	Levosert (levonorgestrel)	TERMINATE IF NOT SELECTED
2	Mirena (levonorgestrel)	
3	Skyla (levonorgestrel)	
4	Liletta (levonorgestrel)	
98	Other [ANCHOR]	

S7. Which of the following intrauterine systems (IUSs) do you have experience removing (with or without replacement)?

Please select all that apply.

1	Levosert (levonorgestrel)	TERMINATE IF NOT SELECTED
2	Mirena (levonorgestrel)	
3	Skyla (levonorgestrel)	
4	Liletta (levonorgestrel)	
98	Other [ANCHOR]	
97	None [ANCHOR, EXCLUSIVE]	

S8. In the past **10 years**, approximately how many intrauterine systems (IUSs) have you prescribed?

#	TERMINATE IF < 2
π	TEMVIIIVATE II \ Z

S9. Since **Levosert (levonorgestrel)** has been available in your country, for approximately **how many** patients have you prescribed and removed (with or without replacement) Levosert (levonorgestrel)?

	Contraception only	Heavy menstrual bleeding (with and without intended contraception)
Total number of Levosert prescriptions	#	# TERMINATE IF < 2
Total number of Levosert removals (with or without replacement)	#	# TERMINATE IF = 0

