# of total patients / month	

- **Q2.** Approximately, how many of your patients are **currently using** one of the following types of contraception by indication?
 - ✓ Oral/pill
 - ✓ Intrauterine device (IUD)
 - ✓ Intrauterine system (IUS)
 - ✓ Hormonal ring
 - ✓ Implant
 - ✓ Injection

	Contraception only	Heavy menstrual bleeding (with and without intended contraception)
# of patients currently using any of the above treatment types	#	#

Q3. Considering **all your patients by indication,** approximately what percentage are currently using the different types of contraception listed below?

	Contraception only	Heavy menstrual bleeding (with and without intended contraception)
Oral/pill	%	%
Intrauterine device (IUD)	%	%
Intrauterine system (IUS)	%	%
Hormonal ring	%	%
Implant	%	%
Injection	%	%
Total	100%	100%

Q4. Considering all your patients currently using intrauterine systems (IUSs) by indication, approximately what percentage are using Levosert (levonorgestrel)?

	Contraception only	Heavy menstrual bleeding (with and without intended contraception)
Proportion of patients currently using IUSs who receive Levosert	%	%

Q5. Considering **all** your patients ever having used and/or currently using **Levosert (levonorgestrel)**, what is the age distribution at the time of prescription, by indication?

	Contraception only	Heavy menstrual bleeding (with and without intended contraception)
16-24 years of age	%	%
25-34 years of age	%	%
35-44 years of age	%	%
45-54 years of age	%	%
55+ years of age	%	%
Total	100%	100%

Q6. When using **Levosert (levonorgestrel)** for **heavy menstrual bleeding (with and without intended contraception)**, what is the average time from insertion to achieving treatment effectiveness (defined as significant reduction in menstrual blood loss)?

1	Less than one month	
2	One to less than two months	
3	Two to less than three months	
4	Three to less than four months	
5	Four months or more	

Q7. In your experience, approximately what percentage of patients using **Levosert (levonorgestrel)** for the following indications need to get it **removed (with or without replacement)** by the end of each year (cumulatively since insertion)?

Please note your responses must be cumulative over time (since insertion).

	Contraception only	Heavy menstrual bleeding (with and without intended contraception)
By the end of Year 1	%	%
By the end of Year 2	%	%
By the end of Year 3	%	%
By the end of Year 4	%	%
By the end of Year 5	%	%

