By the end of Year 6	%	%

VALIDATION MESSAGE REQUIRING TRANSLATION:

ERROR: Please note your responses for each column must be cumulative. For example, your response for the end of year 2 must be equal to or greater than your response for the end of year 1, etc.

Q8. For patients who use **Levosert (levonorgestrel)** for **contraception only** for more than six years, for approximately how many years in total do these patients typically use **Levosert (levonorgestrel)**?

Please feel free to provide a fractional number of years.

	# of years	RANGE 7-10
--	------------	------------

Q9. For patients who use **Levosert** (**levonorgestrel**) for **heavy menstrual bleeding** (with and without **intended contraception**) for more than six years, for approximately how many years in total do these patients typically use **Levosert** (**levonorgestrel**)?

Please feel free to provide a fractional number of years.

	# of years	RANGE 7-10
--	------------	------------

13-02-2023

Q10. Among your patients using Levosert (levonorgestrel) for heavy menstrual bleeding (with and without intended contraception), what percentage would continue to show treatment effectiveness by the end of each year (cumulatively since insertion), while continuing to use the same Levosert (levonorgestrel) device.

Please note your responses must be cumulative over time since insertion.

Treatment effectiveness is defined as significant reduction in menstrual blood loss.

		Heavy menstrual bleeding (with and without intended contraception)
1	By the end of Year 1	%
2	By the end of Year 2	%
3	By the end of Year 3	%
4	By the end of Year 4	%
5	By the end of Year 5	%
6	By the end of Year 6	%
7	Beyond 6 years	%

VALIDATION MESSAGE REQUIRING TRANSLATION:

ERROR: Please note your responses for each column must be cumulative. For example, your response for the end of year 2 must be equal to or less than your response for the end of year 1, etc.

Q11. Considering **all** your patients ever having used and/or currently using **Levosert (levonorgestrel)** for the following indications and who had it removed (with or without replacement), approximately what percentage of these patients had **Levosert (levonorgestrel)** removed for each of the following reasons?

	Contraception only	Heavy menstrual bleeding (with and without intended contraception)
Removed per Schedule (IUS Expiry)	%	%
Planning for family	%	%
Side effects	%	%
Lack of effectiveness	%	%
Menopausal	%	%
Other (specify)	%	%
Total	100%	100%

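### Q7, the only source of the yearly removal likelihoods in the primary endpoint, asks who needs removal, while the endpoint counts every removal; the two should be aligned before fielding

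*Protocol*

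**What the plan says.** Section 10.1 of the Protocol sets the endpoint without limiting it by reason: "Duration of Levosert usage is defined as the difference in time between removal (with or without replacement) and insertion of the device". As there are no patient-level data, the expected duration is built from a removal likelihood for each of Years 1 to 6, plus a final term: "likelihood of Levosert removal beyond Year 6 x total expected usage duration in those patients".

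The items that touch on removal are worded as follows.

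- **Appendix 3, Q7** asks for cumulative percentages by the end of Years 1 to 6 of patients using Levosert who, "for the following indications need to get it" removed. The parenthesis about replacement follows, as in Section 10.1.
- **Section 10.3, item 14** describes the matching output neutrally: "Percentage of Prescribers' patients getting Levosert removed by the end of each year, by indication".
- **Appendix 2, S9** is also neutral: "Total number of Levosert removals (with or without replacement").
- **Appendix 3, Q11** asks about patients who had the device removed. Besides expiry, side effects and lack of effectiveness, it lists "Planning for family", menopause and an open category.
- **Appendix 3, Q8 and Q9** ask for total years of use in patients who go beyond six years, and accept only 7 to 10.

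**The concern.** Only Q7 brings in the idea of need. Nothing in the item tells respondents to include removals that the patient simply chose. A prescriber who takes the word at face value may leave out some removals that Section 10.1 counts, for example some of those under Q11's family-planning, menopausal or other headings.

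No other item can correct this. S9 gives totals without timing, Q8 and Q9 give only the duration of long-term use, Q10 concerns effectiveness, and Q11 gives reasons without years. An analysis plan cannot recover what the question did not ask.

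The study exists because data to support a longer recommended duration in heavy menstrual bleeding are lacking (Section 5.2), and its report goes to the requesting authority (Section 12.6). The main result should therefore measure what Section 10.1 defines.

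**Working it through.** **The plan's own figure.** The Protocol gives no expected value for the endpoint. Its one planning figure, in Appendix 1, Table 3, reproduces. Removals per OB-GYN times the achievable sample gives 227.7 + 429.7 + 68.8 + 95.5, about 821.6 (stated 821), and 55% of that is 451.9 (stated 452). This point does not affect it.

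**Formula.** Let C1 to C6 be the cumulative removal proportions from Q7 and T the answer to Q8 or Q9. Section 10.1 does not name the items, but only these fit. The likelihood in Year i is C_i − C_(i−1), so

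E = Σ i × (C_i − C_(i−1)) + (1 − C6) × T = T − (T − 6) × C6 − (C1 + … + C5).

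T is at least 7, so E rises whenever any C is under-reported and falls whenever any C is over-reported.

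**Inputs.**

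- C1 to C5: Appendix 1 gives retention of "0.94, 0.87, 0.82, 0.76, 0.65, respectively", so cumulative removal is 0.06, 0.13, 0.18, 0.24 and 0.35, with sum 0.96.
- C6 = 0.45: an assumption.
- T = 7: an assumption, the smallest value Q8 and Q9 accept.
- Share of removals left out, f = 10%, 20% or 30%, the same in every year: an assumption.

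**All removals counted.** The yearly likelihoods are 0.06, 0.07, 0.05, 0.06, 0.11 and 0.10. The sum over Years 1 to 6 is 0.06 + 0.14 + 0.15 + 0.24 + 0.55 + 0.60 = 1.74. The tail is 0.55 × 7 = 3.85. E = 5.59 years.

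**Reading 1: chosen removals left out of every year.** The change is f × [(T − 6) × C6 + 0.96].

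| Tail T | Factor | f = 10% | f = 20% | f = 30% |
|---|---|---|---|---|
| 7 | 0.45 + 0.96 = 1.41 | +0.14 | +0.28 | +0.42 |
| 8 | 0.90 + 0.96 = 1.86 | +0.19 | +0.37 | +0.56 |

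Over C6 from 40% to 100% and T from 7 to 10, the rise is 0.14 to 0.50 years for f = 10% and 0.34 to 1.24 for f = 25%.

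**Reading 1, milder form: Years 1 to 5 under-reported, Year 6 correct.** The omitted patients only move to a later year, and the change is f × 0.96: +0.10 for f = 10% and +0.24 for f = 25%.

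**Reading 2: need taken as scheduled expiry.** A prescriber might enter everyone as removed by Year 6, although some keep the device longer. With C1 to C5 unchanged and C6 = 1, E = 1.14 + 6 × 0.65 = 5.04. That is 0.55 years below 5.59. With T = 8 the full-count value is 1.74 + 0.55 × 8 = 6.14, and the shortfall is 1.10.

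**The case against.** The strongest defence is that Q7 carries the same parenthesis about replacement as the endpoint, and that respondents have already met it in S7 and S9, where it covers all removals. In that sequence many will read Q7 as any removal. This stands, and it limits the point to what some respondents may do. It does not remove the point, because the parenthesis says what follows a removal, not why the removal was done.

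It can also be said that a woman who wants to conceive does need a contraceptive device taken out, and that expiry, side effects and lack of effectiveness fit need as well. This too has force: the removals most open to omission may be only some of those in Q11's family-planning, menopausal and other categories.

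A reader might go further and infer any of three things that the document does not support.

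- **That the endpoint is biased upward.** This holds only if removals are omitted. The expiry reading pushes the result down.
- **That each omitted removal is scored as at least 7 years of use.** This holds only if the omission lasts through the Year 6 answer. Otherwise the patient is merely placed in a later year.
- **That the contraception-only column is affected more.** The Protocol gives no removal reasons by indication.

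The translated items are not shown either, so nothing can be said about whether translation strengthens or weakens the word.

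**Conclusion.** The mismatch is real and lies in the item on which the primary endpoint depends. Q7 can be read more narrowly than Section 10.1 and item 14, and no other item can detect or repair the difference.

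The consequence is conditional. Under the assumed inputs, leaving out 10% to 30% of removals overstates duration by 0.14 to 0.42 years, whereas the expiry reading can understate it by 0.55. The omission rates, the Year 6 proportion and the tail are assumptions, so these figures show sensitivity and are not estimates of bias. The document does not allow the size or the net direction to be determined, and no difference by indication is shown. The case for acting is that the change is small and that the ambiguity cannot be removed after fielding.

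**What to change.** Before fielding, reword Q7 along these lines: *approximately what percentage of your patients had Levosert removed for any reason (with or without replacement) by the end of each year (cumulatively since insertion)?* Keep the two indication columns and carry the phrase about any reason into the Czech, Polish, Serbian and Slovakian versions. Item 14 of Section 10.3 is already neutral and needs no change.

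This is a cheap improvement. It adds no question and leaves the sample size as it is. The downside is procedural: under Section 11.2, if the questionnaire has already been approved, the change needs review by the ethics committee in each country before use.

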5 BACKGROUND AND RATIONALE

5.1 Background

Levosert®is a levonorgestrel (LNG)-releasing intrauterine system (IUS) containing 52 mg of levonorgestrel. When inserted into the uterus, it slowly releases this hormone to be absorbed by the user. The initial release of levonorgestrel is approximately 20 micrograms per day. This rate decreases progressively to approximately 8.6 micrograms/day after 6 years. The average in vivo release rate of LNG is approximately 14.3 micrograms/day over a period of 6 years.

In Europe, Levosert is indicated for use in 1) contraception and 2) heavy menstrual bleeding, hereafter referred to as menorrhagia or HMB.

- 1) Contraception. Levosert prevents pregnancy by thinning the lining of the uterus, by making the normal mucus in the opening of the uterus thicker, so that the sperm cannot get through to fertilise the egg and by preventing ovulation in some women.
- 2) Treatment of menorrhagia. The hormone in Levosert acts by thinning the lining of the uterus, so that there is less bleeding every month.

Levosert was first authorised in Europe via Decentralised Procedure (DCP; licence number UK/H/3030/001/DC) on 28 Dec 2012 for the treatment of menorrhagia for three years. Countries targeted for the proposed study (Czech Republic, Poland, Serbia, and Slovakia) authorized Levosert for the treatment of menorrhagia in a separate DCP (HU/H/0580/001/DC) in 2013. The applications were based on a therapeutic equivalence study conducted with Levosert and Mirena®. On 16 Oct 2014, the second indication 'contraception' was approved with new supportive data from the ongoing pivotal Phase 3 study M360-L102. Since then and based on the results of the same Phase 3 study, the duration of use of Levosert for use in contraception extended to 5 years, then to 6 years in all European countries where the product is marketed. However, the ongoing Study M360-L102 was designed to evaluate contraceptive efficacy only (not menorrhagia), and thus, there is need for further evidence regarding usage for the menorrhagia indication to support its use up to the recommended duration determined for the contraception indication.

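### Q8 and Q9 do not limit years of use to one device, so replacement time can inflate the beyond-Year-6 term of the primary endpoint

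*Protocol*

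**What the plan says.** Protocol Section 10.1 sets the unit of the primary endpoint: "Duration of Levosert usage is defined as the difference in time between removal (with or without replacement) and insertion of the device". A removal followed by a replacement therefore closes one duration, and the new device starts another. Expected duration is then built from yearly removal likelihoods for Years 1 to 6 plus a last term, "likelihood of Levosert removal beyond Year 6 x total expected usage duration in those patients".

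Appendix 3 supplies the inputs:

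- **Q7** gives the yearly likelihoods and, as the remainder after Year 6, the beyond-Year-6 likelihood. It counts removals whether or not a replacement follows, cumulatively from insertion, so it is per device.
- **Q8** (contraception only) and **Q9** (HMB) give the duration for the last term. For patients who use Levosert for more than six years, they ask "for approximately how many years in total do these patients typically use" it. Neither question mentions the device, insertion or replacement. Answers must lie between 7 and 10 years.
- **Q10**, on continued effectiveness, restricts its question to patients "while continuing to use the same Levosert (levonorgestrel) device".

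Section 10.3, item 15, reports Q8 and Q9 as "Descriptive statistics on the total duration of use of Levosert in patients who use Levosert for more than six years, by indication", again without a device limit.

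**The concern.** The last term of the endpoint multiplies a per-device likelihood by a duration that, read literally, belongs to the patient. Take a woman whose first Levosert was replaced after 4 or 5 years and who is now in year 8 on her second. She fits the wording of Q8 or Q9 and can be answered as 8 years. Under Section 10.1 she is one completed device of 4 or 5 years and one device still in place.

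Successive devices are plausible here. Section 5.1 says the product was first authorised "for the treatment of menorrhagia for three years", and the longer durations came later and for contraception. Q8 and Q9 also show no option for a respondent without enough experience, which Q12 does offer.

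The study exists because data are lacking on longer use of the product in HMB (Section 5.2). The quantity at stake is how long one device is used. Adding replacement time never shortens the figure given for a patient, so the expected direction is upward. It could not be undone after fielding: Section 9.1 states that no patient-level data are collected, so one-device and multi-device answers could not be told apart.

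**Working it through.** **The plan's own figure.** The protocol states no expected duration. Its only quantitative planning figure is the number of removals covered. From Table 3: 7,400/2,600 × 80 + 16,900/5,900 × 150 + 1,100/1,600 × 100 + 2,100/1,100 × 50 = 227.7 + 429.7 + 68.8 + 95.5 = about 821.6, and 55% of this is 451.9. Both agree with the stated 820 and 450. This point does not change them.

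**Formula.** Write p_i for the likelihood of removal in Year i, s for the likelihood of removal beyond Year 6, and D for the duration from Q8 or Q9. Section 10.1 is then

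E = Σ(i = 1 to 6) i × p_i + s × D.

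All p_i and s come from Q7; only D comes from Q8 or Q9. An error ΔD in D moves E by s × ΔD and leaves every weight unchanged.

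**Inputs.**

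- Retention at Years 1 to 5 from Appendix 1: 0.94, 0.87, 0.82, 0.76, 0.65. Hence p_1 to p_5 = 0.06, 0.07, 0.05, 0.06, 0.11, and p_6 = 0.65 − s.
- D between 7 and 10, from the answer range of Q8 and Q9.
- s is not in the documents. It is assumed to lie between 5% and 65%. The upper end is the Year 5 retention and implies no removals in Year 6.

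**Result.** E = 0.06 + 0.14 + 0.15 + 0.24 + 0.55 + 6 × (0.65 − s) + s × D = 5.04 + s × (D − 6).

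| s (assumed) | E at D = 7 | E at D = 8 | E at D = 10 | 1-year error (s × 1) | Bound (s × 3) |
|---|---|---|---|---|---|
| 5% | 5.09 | 5.14 | 5.24 | 0.05 | 0.15 |
| 10% | 5.14 | 5.24 | 5.44 | 0.10 | 0.30 |
| 20% | 5.24 | 5.44 | 5.84 | 0.20 | 0.60 |
| 30% | 5.34 | 5.64 | 6.24 | 0.30 | 0.90 |
| 50% | 5.54 | 6.04 | 7.04 | 0.50 | 1.50 |
| 65% | 5.69 | 6.34 | 7.64 | 0.65 | 1.95 |

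If s were 0 the effect would be 0. The bound compares two permitted answers, 7 and 10.

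**Mixed answers.** If a fraction m of the women a respondent has in mind are two-device users at 10 years and the rest are at 7, the shift is s × m × 3. With m = 0.5 it is 0.15 years at s = 10%, 0.45 at 30% and 0.75 at 50%.

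**What calendar time allows.** Table 2 shows 99 + 40 + 0 + 3 = 142 devices sold in 2014, which is 0.15% of 96,359. By the end of 2015 it was 11,713 (12%), and by the end of 2016 it was 27,050 (28%). The protocol is dated February 2023 and the study is to last about one year. If fielding is in 2023, nine years of use by the end of that year requires a 2014 device, and eight years requires one from 2014 or 2015.

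**The case against.** The best defence is that the words asking for a total have an ordinary one-device meaning. Q8 follows the Year 6 row of Q7, and a respondent may take the phrase as an instruction to count from insertion rather than report only the years past six. Section 10.1 itself speaks of a total expected duration in those patients, meaning those removed beyond Year 6. This stands to a degree: the wording allows a multi-device reading but does not require it, and nothing in the protocol shows how respondents would answer. It does not remove the gap. Q8 and Q9 drop the qualifiers of Q7, and Q10 shows that the limit was easily written.

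A reader might infer three stronger things that the documents do not support:

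- **That re-fitted women are counted as long-duration users.** They are not. Q7 records their first device as removed in the year of replacement, so they do not enlarge s. Only D can be affected.
- **That multi-device answers will dominate, because only 28% of devices were sold early enough to pass six years.** A woman with more than six continuous years over two devices must also have started in 2014-2016. The same cohort limits both groups, and no replacement rate is given.
- **That typical answers of 9 or 10 years make the error large.** Under the assumed 2023 fielding, only the 142 devices sold in 2014 could support nine years, and none could support ten. The 3-year bound is what the questionnaire permits, not a forecast.

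Nor is the direction guaranteed in every case. If two-device totals were shorter than typical one-device use beyond six years, including them would lower D.

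**Conclusion.** The point holds as a mismatch of unit between Q8 and Q9 on one side and Section 10.1 and Q7 on the other. It can inflate D, and through D the last term of the primary endpoint, by s × ΔD. The bound is 3 years times the beyond-Year-6 share: 0.15-1.95 years for an assumed share of 5-65%. A 1-year overstatement, which sits better with the sales history, gives 0.05-0.65 years. These sizes rest on an assumed share and on respondents answering with multi-device totals; the documents establish neither. The study is descriptive, so no test is affected. The reason to act is that the possible bias lies in the primary endpoint, is likely to favour longer use, and cannot be separated out once the survey has closed.

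**What to change.** Before fielding, reword Q8 and Q9 so that they ask about patients who keep the same Levosert device in place for more than six years. They should ask for the years from insertion to removal of that one device, whether or not it is then replaced, and tell the respondent not to add time on a replacement device. Carry the same limit into analysis item 15 of Section 10.3, which reports these answers. The definition in Section 10.1 is already per device and can stay.

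The cost is re-translation of two questions into four languages and ethics committee review in each country, since Section 11.2 requires approval of any questionnaire change. The sample size and the primary formula do not change.
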